CDAI	Crohn disease activity index
CRF	Case Report Form
CTQT	Clinical Trial Quality Team
DMC	Data Monitoring Committee
DSUR	Development Safety Update Report
GCP	Good Clinical Practice
GP	General Practitioner
Hb	Hemoglobin
IBDQ	Inflammatory bowel disease questionnaire
IDA	Iron deficiency anemia
IG-IBD	Gruppo Italiano per lo Studio delle Malattie Infiammatorie Croniche Intestinali
IMP	Investigational Medicinal Product
MHRA	Medicines and Healthcare products Regulatory Agency
NIMP	Non Investigational Medicinal Product
RA	Regulatory Agency
R&D	Research and Development
REC	Research Ethics Committee
SAE	Serious Adverse Event
SUSAR	Suspected Unexpected Serious Adverse Reaction
TMG	Trial Management Group
TSC	Trial Steering Committee
UC	Ulcerative colitis
VAS	Visual analogue scale

3 Trial Flow Chart

4 Introduction

4.1 Background

Anemia is the most common extraintestinal manifestation of IBD, occurring in 6 to 74 percent of patients. This wide range in the prevalence of anemia is related to differences in study design, in the criteria used to define anemia and to the increasing awareness of anemia in these patients. According to a recent meta-analysis of European studies involving 2192 IBD patients, the overall prevalence of anemia in Europe was 27%, ulcerative colitis patients being less likely to develop anemia than those with Crohn's disease (Filmann et al, 2014). Therefore, anemia represents a significant clinical and social burden in IBD management; this is more evident in southern Europe where the prevalence of anemia is close to 40%.

4.2 Clinical Data

Most cases of anemia in IBD are due to iron deficiency (IDA) and to anemia of inflammation (AI) (Bergamaschi et al, 2010). Guidelines concerning the diagnosis and treatment of IDA in IBD have been published by the European Crohn's and Colitis Organisation (ECCO, Dignass et al, 2015). According to present guidelines iron supplementation should be started when IDA is present or even in the presence of iron deficiency without anemia. A meta-analysis of iron supplementation studies in IBD-associated IDA found that intravenous iron is more effective and better tolerated than oral iron supplementation, but the sample size of the included studies was small (Lee et al, 2012); absolute indications for intravenous iron include severe anemia (haemoglobin <10.0 g/dL) and intolerance or inadequate response to oral iron.

Although the ECCO diagnostic criteria for IDA are simple, and iron supplementation represents a cheap and usually effective treatment, many IBD patients with IDA are not properly treated. The inconsistent adherence, by many physicians, to treatment guidelines for IDA in IBD is often motivated by the belief that mild to moderate degrees of anemia may not have a significant impact on the patient's quality of life or do not represent the main clinical problem of the patient, that oral iron supplementation may adversely affect disease activity, and that parenteral iron administration may cause severe side effects.

4.3 Rationale for Investigation

In order to improve the diagnostic and therapeutic work-up of anemia in IBD, it is necessary to precisely define the prevalence and pathogenesis of anemia in the Italian IBD population and gain informations about how anemic patients, particularly those with IDA, are usually managed and followed-up. In addition, since IDA and AI are the most common forms of anemia in IBD, and both mechanisms often concur to the pathogenesis of anemia in the same subject, stringent diagnostic criteria to distinguish the three conditions (IDA, AI and coexistence of IDA and AI) are urgently needed. The differential diagnosis between IDA and AI is often difficult since inflammation modifies serum ferritin and transferrin saturation (TfSat) that become unreliable as indicators of iron status. Recently, serum hepcidin concentration has been identified as a new index of iron status that can be useful to differentiate IDA and AI in IBD (Bergamaschi et al, 2013; Mecklenburg et al, 2014). Hepcidin, a peptide produced by the liver in response to increased iron stores, inflammation and reduced erythropoietic activity, is the master regulator of body iron homeostasis and acts by inhibiting iron absorption and iron release from hepatocytes and macrophages to plasma (Ganz T, 2011). The potential role of serum hepcidin determination as a diagnostic tool in the differential diagnosis of anemia in IBD and in other inflammatory diseases must be clearly defined. The investigation of these topics is important since a more accurate pathogenetic diagnosis of anemia in IBD, while preventing the useless and potentially

harmful treatment of AI with iron supplementation, might allow the identification and appropriate treatment of IDA patients in the presence of inflammation.

5 Study Design

5.1 Statement of design

We will perform a longitudinal, prospective, observational study whose aim is the determination of the prevalence and pathogenesis of anemia in IBD patients. Anemia is defined according to WHO criteria: Hb <13.0 g/dL for males and Hb <12 g/dL for females (Blanc et al, 1968). Anemia work-up should be initiated whenever Hb concentration is below normal and will include the determination of the laboratory parameters reported in the CRF. A serum ferritin <100 µg/L and transferrin saturation <20% are required for the diagnosis of isolated IDA and for the association of IDA and inflammation.

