6.5.2 Secondary objectives

Secondary objectives of the study are a) to investigate the pathogenesis of anemia in IBD, with a particular focus on the differential diagnosis between IDA and AI, and how disease activity, extension or behavior influence the relative frequency of IDA and AI; b) to verify the adherence to ECCO guidelines for the treatment of IDA in IBD (the proportion of patients with IDA that receive adequate iron supplementation); c) to administer dedicated questionnaires to the patients in order to measure the influence of anemia on fatigue and quality of life among IBD patients.

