5.6.2 Secondary outcome measure

1. Relative prevalence of IDA and AI in IBD will be computed as the ratio between the number of patients with IDA or with AI over the total number of anemic patients
2. Influence of anemia on fatigue and quality of life among IBD patients. Quality of life will be evaluated using the validated Italian translation of the Inflammatory Bowel Disease Questionnaire (IBDQ, Cicciocioppo et al, 2011), whereas the effect of anemia on fatigue will be measured using a Visual Analogue Scale.
3. Influence of anemia on hospitalizations, additional outpatient visits, number of endoscopic examinations and further treatments will be assessed through the analysis of correlations between the degree of anemia and the relevant parameters.

6 Selection and withdrawal of subjects

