Evaluation of the global prevalence of anemia in IBD
Secondary objectives

 1. Evaluation of the pathogenesis of anemia in IBD 2. Evaluation of adherence to ECCO guidelines for the treatment of IDA in IBD 3. Influence of anemia on fatigue, quality of life, hospitalizations, additional outpatient visits, number of endoscopic examinations and further treatments
Primary outcome measure
Prevalence of anemia will be determined according to the WHO criteria for the diagnosis of anemia: Hb <13.0 g/dL for males and Hb <12 g/dL for females
Secondary outcome measure

 1. Anemia differential diagnosis: the main objective is to differentiate IDA and AI; this will require that serum ferritin >100 µg/L and transferrin saturation ≤ 20% for AI, serum ferritin ≤100 µg/L and transferrin saturation ≤20% or serum ferritin ≤30 µg/L for isolated IDA and for the association of IDA and inflammation 2. To evaluate how many IBD patients with IDA actually receive any form of iron supplementation and which iron supplementation modalities are more commonly used 3. Quality of life and fatigue will be assessed by the IBDQ score (Ciccocioppo et al, 2011) and the visual analogue scale (VAS), respectively

Table 2. Precision that can be obtained in the evaluation of the prevalence of anemia in IBD, depending on the number of patients screened for anemia and on the prevalence of anemia

Hypothesis	Screened patients	Prevalence expected % (95% CI)	Precision %
1	5000	25 (23.8-26.2)	2.4
2	5000	40 (38.6-41.4)	2.8
3	8000	25 (24.1-26.0)	1.9
4	8000	40 (38.9-41.1)	2.2

CI: confidence interval

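### Section 5.1 and Table 1 define iron deficiency anemia (IDA) by different rules; the ferritin ≤30 µg/L route exists only in Table 1, so the secondary IDA outcomes depend on which rule is applied.

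*Protocol*

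**What the plan says.** Section 5.1 (Statement of design) states: "A serum ferritin <100 µg/L and transferrin saturation <20% are required for the diagnosis of isolated IDA". The same sentence extends the requirement to IDA combined with inflammation: "transferrin saturation <20% are required for the diagnosis of isolated IDA and for the association of IDA and inflammation". It offers no other route to the diagnosis.

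Table 1, secondary outcome measure 1, covers the same two categories with a different rule: "serum ferritin ≤100 µg/L and transferrin saturation ≤20% or serum ferritin ≤30 µg/L for isolated IDA and for the association of IDA and inflammation". Table 1 also holds the only rule for anemia of inflammation (AI): "serum ferritin >100 µg/L and transferrin saturation ≤ 20% for AI".

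IDA status feeds these results:

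- Section 5.6.2, outcome 1, is "the ratio between the number of patients with IDA or with AI over the total number of anemic patients".
- Section 6.5.2, objective b, concerns "the proportion of patients with IDA that receive adequate iron supplementation". Table 1 words its counterpart as "To evaluate how many IBD patients with IDA actually receive any form of iron supplementation". Both count among patients with IDA.
- Sections 5.3 and 10 plan comparisons of IDA and AI prevalence across patient and disease characteristics, and analyses of variables associated with type of anemia.

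**The concern.** Section 5.1 words its two conditions as compulsory, so Table 1's ferritin ≤30 µg/L route cannot be read as an elaboration of it. Section 5.5 points to Table 1 for objectives and outcome measures, while section 5.1 is the statement of design. Neither is obviously subordinate, and no text ranks them.

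The same data could therefore give two IDA shares and two adherence bases. That matters in a study whose rationale (section 4.3) rests on separating IDA, AI and their coexistence, and which plans at least 60 centers. The protocol has not left a detail open here: it states two incompatible rules, and any later plan has to depart from one of them.

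**Working it through.** The protocol gives no expected IDA share, only 80 to 90% for iron deficiency and/or AI together (sections 5.3 and 10). There is no stated figure to reproduce, so the check compares the rules.

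**The two rules (ferritin F in µg/L, transferrin saturation S in %)**

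- Section 5.1: F < 100 and S < 20.
- Table 1: (F ≤ 100 and S ≤ 20) or F ≤ 30.
- AI, Table 1 only: F > 100 and S ≤ 20.

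**Direction.** Any patient with F < 100 and S < 20 also has F ≤ 100 and S ≤ 20. Section 5.1 is thus contained in Table 1, and every discordant patient is IDA under Table 1 only.

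| F / S | Section 5.1 | Table 1 | AI rule |
|---|---|---|---|
| 15 / 12 | IDA | IDA | no |
| 25 / 24 | not IDA | IDA | no |
| 60 / 20 | not IDA | IDA | no |
| 100 / 15 | not IDA | IDA | no |
| 101 / 15 | not IDA | not IDA | AI |
| 60 / 25 | not IDA | not IDA | no |

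Over whole-number values (F 1 to 300, S 1 to 60) there are 1319 discordant combinations, all IDA in Table 1 only. Of these, 1230 have F ≤ 30 and S ≥ 20 (30 × 41); the other 89 lie exactly on a cut-off. These count combinations, not patients. They show that the ferritin ≤30 route is the substantive difference and that strict versus inclusive cut-offs matter only at exact values.

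The AI count does not change with the IDA rule. Under section 5.1 the discordant patients are neither IDA nor AI.

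**Size for the IDA share.** With N = 2000 anemic patients (section 5.3) and a discordant fraction q:

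- Extra IDA patients under Table 1 = 2000 × q. At q = 1% this is 20 patients, or 1 point of IDA share.
- Sampling half-width at a share of 50%: 1.96 × √(0.5 × 0.5 / 2000) = 0.0219, or 2.19 points. At 60% it is 2.15, and at 70% it is 2.01.
- The shift equals 2.19 points at q of about 2.19%, or 0.0219 × 2000 ≈ 44 patients.

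For assumed q:

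- 0%: no shift.
- 2%: 40 patients, 2 points.
- 5%: 100 patients, 5 points.
- 10%: 200 patients, 10 points.

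The half-width is only a yardstick: both rules would be applied to the same patients, so the gap between them does not shrink with more patients.

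**Size for adherence.** Assume 1200 IDA patients under section 5.1 (60% of 2000). The base becomes 1240, 1300 or 1400 at q = 2, 5 or 10%. The proportion treated moves only if discordant patients are treated at a different rate. If 60% of the concordant and 30% of the discordant were treated (assumed), then at q = 5% it is (0.6 × 1200 + 0.3 × 100) / 1300 = 750 / 1300 = 57.7% instead of 60%. With equal rates it stays at 60%.

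**The case against.** The strongest reply is that little is at risk. The primary outcome rests on hemoglobin alone, and neither it nor the precision in Table 2 uses an IDA rule. Ferritin, serum iron and transferrin are mandatory at baseline (section 8.2), so either rule can be applied later to every patient with complete data. Table 1 is the natural home of an outcome definition, and a statistical analysis plan that is not at hand may settle the matter. All of this stands and lowers the severity. It does not remove the contradiction, since no text gives Table 1 precedence.

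A reader might go further in several ways that the document does not support:

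- **That the shift exceeds sampling error.** This needs a discordant share above about 2.2%, and nothing in the protocol gives that share. Values near zero are as admissible as larger ones.
- **That the mismatched cut-offs leave a serious gap at ferritin 100 µg/L.** The gap appears only when the section 5.1 IDA rule is paired with the Table 1 AI rule; section 5.1 has no AI rule. It affects exact values only.
- **That Table 1 must be right because it leaves no gap against its AI rule.** Moving the AI cut-off would close the gap equally well. Whether ferritin ≤30 µg/L alone establishes IDA is a clinical question.
- **That section 5.6.2 also conflicts.** It gives no cut-offs.
- **That centers will supply conflicting labels, or that the rule will be picked after results are seen.** Both are possible, but the protocol describes neither.

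**Conclusion.** The contradiction is real and can be read directly from the text. Its substance is the ferritin ≤30 µg/L route, present in Table 1 and excluded by the compulsory wording of section 5.1. Table 1 always yields at least as many IDA patients, so the IDA share and the adherence base can only be equal or larger under it. The adherence proportion itself may move either way or not at all. Analyses of type of anemia inherit the same reclassification.

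The size cannot be computed from the protocol. The scale of 20 patients, or 1 point, per 1% discordant assumes that the expected 2000 anemic patients are enrolled and have complete iron tests. The 2.2-point half-width assumes an IDA share near 50% and a simple binomial interval. Since only secondary outcomes are touched and the data for either rule are collected, this is a should-fix point.

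**What to change.** Reconcile section 5.1 and Table 1 to a single IDA rule before analysis, stated identically in both places, with cut-offs that meet the AI rule without a gap or an overlap. Which rule is right is for the sponsor's clinical judgement; this review takes no position.

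Derive the class centrally from the recorded baseline ferritin, serum iron and transferrin. Report the IDA share and the adherence result under the other rule as a sensitivity analysis, with the number of patients reclassified, so that readers can see the effect that cannot be computed now.

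The cost is a short amendment, one derived variable and one extra set of table rows. No new data are needed, and the sample size and the primary analysis do not change.

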5.2 Number of Centers

We plan to involve at least 60 IG-IBD Centers in this observational study.

5.3 Number of Subjects

We expect to include 2000 anemic patients in the study; approximately 80 to 90% of these patients will have some form of iron deficiency and/or AI. This will allow to evaluate differences in prevalence of IDA and AI according to gender, age, diagnosis, time from diagnosis, presence of inflammation, activity, extension and behaviour of the disease, and to evaluate variables associated with type and severity of anemia in both univariate and multivariate analysis.

5.4 Participants Study duration

Expected duration of subject participation to both the observational and the therapeutic trials will be 24 weeks; all anemic patients recruited in the study will undergo screening to investigate the mechanism of anemia, and follow-up evaluation will be performed at weeks 4, 12 and 24. At follow-up, informations about the treatment of anemia, fatigue and quality of life must be collected.

5.5 Study objectives

Table 1 summarizes study objectives and outcome measures.

6.5.1 Primary objective

Primary endpoint of this observational study is to determine the prevalence of anemia in Italian patients with IBD.

6.5.2 Secondary objectives

Secondary objectives of the study are a) to investigate the pathogenesis of anemia in IBD, with a particular focus on the differential diagnosis between IDA and AI, and how disease activity, extension or behavior influence the relative frequency of IDA and AI; b) to verify the adherence to ECCO guidelines for the treatment of IDA in IBD (the proportion of patients with IDA that receive adequate iron supplementation); c) to administer dedicated questionnaires to the patients in order to measure the influence of anemia on fatigue and quality of life among IBD patients.

5.6 Study Outcome Measures

5.6.1 Primary outcome measure

The primary outcome will be computed as the ratio of the number of anemic patients over the number of patients screened for anemia together with its 95% confidence interval.

5.6.2 Secondary outcome measure

1. Relative prevalence of IDA and AI in IBD will be computed as the ratio between the number of patients with IDA or with AI over the total number of anemic patients
2. Influence of anemia on fatigue and quality of life among IBD patients. Quality of life will be evaluated using the validated Italian translation of the Inflammatory Bowel Disease Questionnaire (IBDQ, Cicciocioppo et al, 2011), whereas the effect of anemia on fatigue will be measured using a Visual Analogue Scale.
3. Influence of anemia on hospitalizations, additional outpatient visits, number of endoscopic examinations and further treatments will be assessed through the analysis of correlations between the degree of anemia and the relevant parameters.

6 Selection and withdrawal of subjects

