6.2 Subject withdrawal criteria

At anytime during the study, participating subjects may ask to be withdrawn from the study. Withdrawn subjects can be followed up for their IBD at the same participating Center where they were initially enrolled. Withdrawn subjects will not be replaced.

7 Concomitant therapy

Nutritional supplementation with iron and/or vitamin integrators containing folic acid or vitamin B12, as well as any other treatment of IBD and relative comorbidities are allowed during the study.

8 Procedures and assessments

Laboratory assessments can be performed outside the participating Centers, and results faxed or emailed to the Investigators who will register data in the eCRF. Result notification to the trial team must be performed as soon as possible.

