8.4 Long-Term Follow-up Assessments

After the end of the study patients will be followed-up as usual for patients with their conditions. Telephone calls will be used to contact patients if visits or data collection time-points are missed; whenever data collection will be impossible, the patient will be identified as 'lost to follow-up'.

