8.6 Schedule of Assessments

A format of all study-related assessments is included in the CRF.

9 Evaluation of Results (Definitions and response/evaluation of outcome measures)

The primary end-point of the observational study (prevalence of anemia) will be evaluated at patient recruitment. Other informations concerning laboratory parameters, quality of life and clinical course will be collected at the scheduled follow-up visits.

10 Statistical methods and number of Subjects to be enrolled

If at least 60 IG-IBD Centers will participate to the study, 5000 to 8000 IBD patients will be screened for anemia within 6 to 12 months from the start of the study. Since anemia affects 25% to 40% of IBD patients, we expect to include 2,000 anemic patients for this observational study. For the first endpoint (the prevalence of anemia) the precision that can be obtained, based on this hypothesis, is summarized in Table 2. Approximately 80 to 90% of these patients will have some form of iron deficiency and/or AI. This will allow to evaluate differences in prevalence of IDA and AI according to gender, age, diagnosis, time from diagnosis, presence of inflammation, disease activity, extension and behavior, and to evaluate variables associated with type and severity of anemia in both univariate and multivariate analysis.

Multivariable models will be fitted to assess the role of anemia on the outcome, while adjusting for potential confounders. Linear regression, logistic regression or Poisson regression models will be used depending on the outcome distributions. Descriptive statistics will be computed overall and by anemia groups.

11 Definition of the end of the study

The competent authority and Ethics Committee will be notified of the end of the clinical study within 90 days of its completion. The end of study will be the date of the last patient's last visit.

12 Data handling and record keeping**13.1 CRF**

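### Resource use is to be analysed by correlation in section 5.6.2 and by regression in section 10; neither relates events to time observed, so the association can be biased if leaving depends on severity of anemia

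*Protocol*

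**What the plan says.** Protocol section 5.6.2, item 3, lists as a secondary outcome "Influence of anemia on hospitalizations, additional outpatient visits, number of endoscopic examinations and further treatments", and plans to assess this by "analysis of correlations between the degree of anemia and the relevant parameters". It names no coefficient, no rate, no denominator of observed time and no window over which events are collected.

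Protocol section 10 says that multivariable models will assess the role of anemia while adjusting for confounders: "Linear regression, logistic regression or Poisson regression models will be used depending on the outcome distributions". It does not say which outcome goes with which model, and it mentions neither an offset nor observed time.

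On follow-up, section 5.4 says: "Expected duration of subject participation to both the observational and the therapeutic trials will be 24 weeks", with visits at weeks 4, 12 and 24. Section 6.2 allows early departure: "At anytime during the study, participating subjects may ask to be withdrawn from the study", without replacement. Section 8.4 has missed visits chased by telephone; "whenever data collection will be impossible, the patient will be identified as" lost to follow-up. How the events of such a patient enter the analysis is not stated.

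**The concern.** Hospitalizations, additional visits and endoscopies are events that accumulate with time. A correlation between severity and the number of events has no place for the time over which the events were counted. A patient seen for 4 weeks without an admission scores the same as one seen for 24 weeks without one.

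If more severely anemic patients leave earlier, their counts are cut short, and a real association shrinks or a spurious inverse one appears. If they stay longer than mildly anemic patients, the association is inflated. Adjustment for disease activity does not in itself correct for unequal observation, and a Poisson model without an offset has the same problem. At stake is whether the study can say how strongly anemia is associated with use of care.

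The two sections also point to different analyses of the same question, and only the regression in section 10 can carry observed time.

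**Working it through.** The protocol gives no figure for resource use, so there is none to reproduce.

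**Inputs from the protocol.** 2000 anemic patients (sections 5.3 and 10); 24 weeks of planned participation (section 5.4); withdrawal at any time (section 6.2).

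**Inputs assumed, because the protocol gives none.** Events are counted over follow-up. They are Poisson at a constant rate. Leaving times are uniform over the 24 weeks, and leaving is unrelated to events given severity.

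**Step 1: the mechanism.** If a share d of patients leaves at uniform times, the mean observed fraction of the 24 weeks is 1 − d/2.
- Mildest patients, d = 5%: 1 − 0.025 = 0.975.
- Most severe patients, d = 25%: 1 − 0.125 = 0.875.
- Ratio: 0.875/0.975 = 0.897.

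With no true effect, unadjusted counts are thus about 10% lower in the most severe than in the mildest patients. If d is the same at every severity, the ratio is 1 and no false association arises.

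**Step 2: check of the formula.** A simulation used severity uniform from −1 to 1, 0.5 events per 24 weeks, and leaving times uniform from 0.02 to 1 of the period. The mean time lost per leaver is then 1 − 0.51 = 0.49, and the observed fraction is 1 − 0.49d. Severity spans 2 units, so the distortion per unit is the square root of the ratio of the two fractions.

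| Leaving, mildest to most severe | Observed fractions | Factor per unit | True 1.5 becomes (formula) | Simulated, no offset | Simulated, offset |
|---|---|---|---|---|---|
| 5% to 15% | 0.976, 0.927 | 0.975 | 1.46 | 1.45 | 1.49 |
| 10% to 30% | 0.951, 0.853 | 0.947 | 1.42 | 1.42 | 1.50 |
| 10% to 50% | 0.951, 0.755 | 0.891 | 1.34 | 1.33 | 1.50 |
| 30% to 10% | 0.853, 0.951 | 1.056 | 1.58 | 1.58 | 1.50 |

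Formula and simulation agree. The bias runs in both directions, and the offset removes it. With leaving of 10%, 20% or 30% unrelated to severity, the rate ratio without offset stays at 1.49 to 1.50, and the correlation weakens only from about 0.16 to 0.158, 0.154 and 0.147.

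**Step 3: on the Hb scale.** Further assumptions: Hb normal with SD 1.6 g/dL and 30% of patients below the cut-off; Spearman test of severity against the count; leaving 5% to 25% unless stated.
- No true effect: the correlation test rejects in about 25% to 28% of studies at 1 event per 24 weeks and in 46% to 52% at 2 events, against 5% to 7% with the offset.
- True rate ratio 1.10 per 1 g/dL lower Hb, 1 event: the estimate without offset is about 1.06, a factor of 1.062/1.10 = 0.965. Power of the correlation test is about 34%, against 93% for regression with the offset. Without any leaving the two have 90% and 95%, so only a small part of the gap comes from the choice of test.
- Leaving 5% to 40%: 1.10 reads as about 1.03.
- Leaving 15% at every severity: rejection of a true null is about 5% to 6%.

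**Step 4: milder cases, no true effect.** Leaving 5% to 15% at 1 event gives rejection of about 8% to 9.5%; 5% to 10% at 1 event, 5.5%; 5% to 25% at 0.2 events, 9.8%; 5% to 15% at 0.3 events, 6.8%.

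**Step 5: completers only.** With leaving 5% to 25% and no true effect, the correlation test in patients with full follow-up rejects in 4% to 5%. At a true 1.10 its power is about 80% to 82%, against 93% to 94% for all patients with the offset. Here the loss is in precision; there is no bias under these assumptions.

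**The case against.** The strongest reply has four parts.

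First, the protocol does not say that unadjusted counts will be correlated. It speaks only of the relevant parameters, and further treatments need not be a count. That stands: counts are the natural reading of the list, but an inference.

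Second, nothing says that truncated follow-up is entered as if complete. The lost-to-follow-up label fits equally well with leaving such patients out, and then no false association appears in these simulations. That also stands, and the bias must be stated as conditional; what remains on that reading is the loss of precision in step 5.

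Third, section 10 already allows Poisson regression, and an offset is a detail that a statistical analysis plan, not at hand here, may supply. This stands in part. A missing offset alone would be no finding. But section 5.6.2 names a method for this outcome, and that method cannot use observed time; section 10 does not assign its models to this outcome. The two need to be aligned.

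Fourth, the offset is not perfect. If half the events fall in the first 4 weeks (an assumption), the offset analysis itself rejects a true null in 10% to 14% of studies, with a rate ratio of about 1.02. Leaving prompted by events is also not corrected. Both are limits of the remedy.

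A reader might infer that the planned analysis is certain to read short observation as low use and therefore to give a biased association. The documents do not support that: they give no dropout rate, no event rate and no link between leaving and severity.

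**Conclusion.** The point holds in conditional form. Section 5.6.2 names correlation and section 10 names regression for what appears to be the same question, and neither relates events to observed time although early departure is allowed. Three cases follow. If partial follow-up is treated as complete and leaving depends on severity, the estimate can be biased towards or away from no effect; the shift from 1.10 to about 1.06 illustrates this under assumed leaving of 5% to 25% and 1 event per 24 weeks. If only completers are used, precision is lost. If leaving is unrelated to severity, no false association arises and the correlation is only slightly attenuated. Which case applies cannot be told from the protocol, and with smaller gradients or rarer events the effect is small.

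Priority is minor. Resource use is a secondary outcome: it appears in section 5.6.2 and among the objectives in Table 1, but not in the secondary objectives of the main text or the outcome measures of Table 1. The primary endpoint, prevalence of anemia, is evaluated at recruitment and is unaffected.

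**What to change.** In section 5.6.2 item 3, for the outcomes that are counts, replace the correlations by a reference to the count regression of section 10: Poisson, or negative binomial if the counts are overdispersed, with the log of time under observation (recruitment to last contact, at most 24 weeks) as offset, adjusted for confounders. Report the rate ratio per 1 g/dL lower Hb with its 95% CI. Patients with partial follow-up then contribute the time for which they were seen. State the same offset in section 10.

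The cost is one sentence in each section and a last-contact date per patient, which visit and withdrawal records should supply. No extra patients or procedures are needed. The small downside is that the offset assumes a roughly constant event rate over the observed time and leaving unrelated to events given the covariates.
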